### **Lesion detectability**

For all lesions that are detected on both scans, we will compare all parameters (such as lesion SUVmean, SUVmax and contrast) measured on conventional and digital PET. Differences between conventional and digital PET will be assessed using the Wilcoxon signed-rank test.

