### 2.2 Secondary objectives: image quality

*What is the image quality (in both quantitative and qualitative terms) of digital PET as compared to conventional PET?*

- 2.1 How do experienced readers rate digital PET image quality?
- 2.2 How does digital PET influence diagnostic confidence for N- and M-staging?
- 2.3 Are there differences in the appearance of normal tissues between digital and conventional PET?
- 2.4 What is the lesion detectability for digital PET as compared to conventional PET?
- 2.5 What is the optimal cut-off value of tumor uptake or lesion contrast to distinguish between benign and malignant lesions for digital PET, and how does this compare to conventional PET?
- 2.6 What are the optimal settings for digital PET to fulfill EANM procedure guidelines?
- 2.7 Do conventional and digital PET/CT studies, that both fulfill EANM procedure guidelines, provide comparable final PET/CT results?

Both the set of primary and secondary objective research questions can be studied in a variety of subgroups, based on tumor type, lesion size or other clinical factors.

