### **3. STUDY DESIGN**

We will perform a single center diagnostic accuracy study, in which patient-scans obtained using two types of PET/CT scanners (1 clinical study on the conventional system and 1 clinical study on the digital system) will be intra-individually compared.

Patient selection will be performed at the NM department in Isala. Patient eligibility will be based on the information provided by the referring specialist on the requisition for the clinical FDG-PET/CT study.

Patients will be included during the inclusion period of 6-12 months. Patients that meet the inclusion criteria and have signed informed consent will undergo two PET/CT scans on both the conventional and the digital PET system, immediately after each other. The scan order will be randomized per week:

- Week 1: first scan on conventional PET/CT, second scan on digital PET/CT.
- Week 2: first scan on digital PET/CT, second scan on conventional PET/CT. Etc.

For each patient, we start with a separate analysis of conventional and digital PET/CT images. One investigator will evaluate the PET/CT images quantitatively while two NM physicians will give qualitative (visual) judgments. Afterwards, we compare conventional and digital findings for all patients.

PET/CT data will be analyzed based on three subgroups of patients with lung cancer, breast cancer and esophageal cancer respectively. Pathology results and follow-up imaging by PET, CT, echography and MRI will be used as gold standard. When validation results are not available, conventional and digital PET/CT results are just compared with each other. More information on data analysis is described in section 5.2.

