### **5.2.3 Validation**

For each patient, the results of the PET/CT studies will be compared with available validation results. It is preferred that this regards invasive staging with pathology (PA) evaluation, although it may also include follow-up or information from other imaging modalities such as MRI and contrast-enhanced CT. Validation shall be performed based on findings from both conventional and digital PET/CT.

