#### 7.1.1 Primary objective: diagnostic outcome of the PET/CT studies

For each patient separately, the diagnostic outcome for the conventional and digital PET/CT study will be compared. Measured ordinal differences in for example the N-status or the TNM classification will be assessed based on two methods. The first method is based on the sign test, in which the comparison results in an agreement or a disagreement. The second method is based on the Wilcoxon signed-ranked test, in which the amount of disagreement is also taken into account. Moreover, we will calculate agreement percentages on the diagnostic outcome between both systems. Furthermore, using validation results as a reference, we will determine the sensitivity, specificity and accuracy for both NM physicians based on the following formulas:

$$\text{Sensitivity} = N_{PET \text{ positive}} / N_{\text{true positive}}$$

$$\text{Specificity} = N_{PET \text{ negative}} / N_{\text{true negative}}$$

$$\text{Accuracy} = (N_{PET \text{ positive}} + N_{PET \text{ negative}}) / (N_{\text{true positive}} + N_{\text{true negative}})$$

To test whether differences in sensitivity, specificity and accuracy between conventional and digital PET/CT are significant, we will apply the McNemar paired proportion test. A p value of less than 0.05 will be considered to indicate statistical significance.

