**Inter-observer agreements**

Two NM physicians will evaluate conventional and digital PET/CT images on final diagnostic outcome, general image quality and diagnostic confidence. To evaluate the inter-observer variation between these two operators, we will compare percentage agreements and calculate a kappa.

Both the set of primary and secondary study parameters will be studied in a variety of subgroups, based on tumor type, lesion size and other clinical factors.

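### Lesion-level tests in section 7.1.2 make no allowance for several lesions per patient, and the lesion detectability comparison is conditional on detection by both scanners

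*Combined protocol and SAP*

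**What the plan says.** Objective 2.4 (section 2.2) asks "What is the lesion detectability for digital PET as compared to conventional PET". Section 5.3.2 then lists what is measured under lesion detectability: SUV values, volume, contrast, contrast-to-noise and ratios to liver and aorta, set against CT diameter. The analysis in section 7.1.2 reads "For all lesions that are detected on both scans, we will compare all parameters (such as lesion SUVmean, SUVmax and contrast", followed by "Differences between conventional and digital PET will be assessed using the Wilcoxon signed-rank test". No significance level is given there.

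The next paragraph, Optimal cut-off values, uses ROC curves and the McNemar test at p below 0.05 on lesion SUVmean, SUVmax and contrast, to separate benign from malignant lesions. Section 7.1 foresees both lesion-based and patient-based comparisons, and section 5.2.2 measures every lesion. Nothing in the document mentions within-patient correlation, a clustered test, a mixed model or a limit of one lesion per patient.

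Detection itself is handled under the primary objective. Section 7.1.1 says "For each patient separately, the diagnostic outcome for the conventional and digital PET/CT study will be compared" and "using validation results as a reference, we will determine the sensitivity, specificity and accuracy for both NM physicians", with McNemar for the accuracy measures. Section 5.2.3 adds "Validation shall be performed based on findings from both conventional and digital PET/CT". Section 3 adds "When validation results are not available, conventional and digital PET/CT results are just compared with each other". The closing sentence of section 7.1.2 says that the study parameters "will be studied in a variety of subgroups, based on tumor type, lesion size and other clinical factors".

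Section 5.2.2 also has both readers score each selected lesion on both datasets on a four-level visibility scale. Its lowest level means that the lesion is not visualised. Section 7 names no test for this score.

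**The concern.** The signed-rank and McNemar tests assume independent pairs. Lesions of one patient are unlikely to be independent here. They share one interval between the scans, which section 5.1.4 puts at about 21 to 47 minutes depending on the patient, and one scan order, which section 3 sets by week. If the delay or the order changes uptake, it tends to push all of a patient's digital-minus-conventional differences in the same direction. The plan itself expects delay to influence normal tissue uptake (section 7.1.2, Normal tissue appearance). Treating such lesions as independent overstates the information and makes the p-values too small.

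A second, lesser matter concerns what the detectability result can show. Among lesions found on both scans, detection is complete on each scanner by construction. A lesion seen on one scanner only cannot enter that comparison.

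**Working it through.** **Figures in the plan.** None is given for objective 2.4; section 4.4 sizes only objectives 1.1 and 1.3. Those sizes reproduce as exact two-sided sign tests if the stated differences of 20% and 16% are read as 0.70 and 0.66 against 0.50: 49 (power 81.0%), 79 (80.7%), 28 (68.3%) and 42 (66.0%). They count patients, so lesion clustering does not touch them.

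**Inputs for the lesion-level check.**
- From the plan: the 5% threshold of section 7.1.1 and of Optimal cut-off values.
- From the plan: targets of 225 patients overall, 90 each for lung and breast, and 45 for esophageal cancer. Section 4.4 expects about 10% negative scans, leaving about 202, 81 and 40 patients with lesions.
- Assumed, because the documents give neither: m = 2, 3 or 5 lesions per patient, and a within-patient correlation (ICC) of the between-scanner differences of 0.1 to 0.5.

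**Formula.** Pooling understates the variance by the design effect 1 + (m − 1) × ICC. Hence

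type I error = 2 × [1 − Φ(1.96 / √(1 + (m − 1) × ICC))].

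Example: m = 5 and ICC = 0.5 give a design effect of 3.0; 1.96/√3 = 1.13; the two-sided error is 25.8%.

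| Lesions per patient | ICC 0.1 | ICC 0.2 | ICC 0.5 |
|---|---|---|---|
| 2 | 6.2% | 7.4% | 11.0% |
| 3 | 7.4% | 9.8% | 16.6% |
| 5 | 9.8% | 14.4% | 25.8% |

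With m = 1 or ICC = 0 the result is 5.0%.

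**Simulation with no true difference.**
- Pooled Wilcoxon signed-rank, ICC 0.1 / 0.5, 81 patients: 6.1% / 10.6% (m = 2), 6.8% / 16.0% (m = 3), 9.7% / 25.9% (m = 5). Across 202, 81 and 40 patients the range is 6.0% to 25.9%. The same test on patient means gives 4.6% to 5.3%.
- Pooled McNemar, uncorrected asymptotic form, 20% discordant lesions assumed, 202 and 81 patients: 6.1% to 26.1%. A clustered McNemar, with its variance taken from patient sums, gives 4.7% to 5.4%.
- Pooled McNemar, exact form: about 4% to 5% at m = 2 and ICC 0.1, rising to about 23% to 25% at m = 5 and ICC 0.5. The exact test starts below its nominal level, so mild correlation only uses up its conservatism.
- In a variant with the correlation placed on an underlying continuous scale, exact McNemar with 81 patients ranged from about 5% to 19%.

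**Co-detection, with assumed counts for illustration only.** Take 200 lesions seen on both scans, 25 on digital only and 5 on conventional only. The detectability paragraph leaves out 30 of 230 lesions (30/230 = 13%). Had the 30 split 15 and 15, it would analyse exactly the same 200 lesions. The two cases differ completely on detection and not at all in that analysis. The documents do not give the real share of lesions seen on one scan only, so no size is claimed.

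**The case against.** The strongest reply is that section 5.3.2 defines lesion detectability by uptake, volume, contrast and ratios. Measured against that definition, the comparison does what was intended, and a paired test of SUV needs a value from both scans. This stands. A reader might infer that objective 2.4 is left unanswered; the documents do not support that.

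A reader might also infer that the trial never compares detection. It does. Section 2.1 is about detection, numbers of metastases, stations and systems are compared per patient, and sensitivity is tested against the reference. What remains is narrower. Per-patient counts can agree while the lesions differ, no paired lesion-level test of visibility is named, and the score that could supply one has no analysis.

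On clustering, the reply is that the plan does not say lesions are pooled, that lesions per patient and the correlation are assumed, and that the McNemar inflation depends on the version, which the plan does not name. Sensitivity also uses only reference-positive lesions and specificity only reference-negative ones, so each McNemar test has fewer lesions per patient than the total. All of this bears on the size, and at the low end the exact McNemar test is not inflated. It does not remove the point for the Wilcoxon test, which the text applies to all co-detected lesions.

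Finally, section 1 presents the study as an initial assessment, and these objectives are secondary and unsized. That limits the consequence.

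**Conclusion.** The clustering point holds for the lesion-level tests under Lesion detectability and Optimal cut-off values. If lesions are pooled, a nominal 5% test has a type I error of about 6% to 26% for Wilcoxon, about 6% to 26% for asymptotic McNemar and about 4% to 25% for exact McNemar. These ranges rest on an assumed 2 to 5 lesions per patient and a correlation of 0.1 to 0.5, and they fall to the nominal level or below with one lesion per patient or no correlation. Patient-level or clustered versions stay close to 5%.

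It would go too far to conclude that the trial's main p-values are inflated: the primary sign tests compare patients, and their sample sizes are unaffected.

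The secondary point is one of labelling and completeness. The detectability comparison matches its definition in section 5.3.2, but it is conditional on co-detection and cannot show lesions seen on one scanner only.

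**What to change.** In the Lesion detectability and Optimal cut-off values paragraphs, state the unit of analysis. For every lesion-level test, replace the pooled test with one on patient-level summaries or with a patient-clustered version: clustered signed-rank, clustered McNemar, GEE or a bootstrap that resamples patients. Name the McNemar version. The cost is plan wording, a little more analysis work and somewhat larger p-values. No extra patients or scans are needed.

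Label the detectability result as conditional on detection by both scanners. Add an analysis of the visibility score of section 5.2.2, level 1 against levels 2 to 4, per reader, clustered by patient and broken down by CT diameter. Describe it as a comparison of visibility, because readers score lesions that have already been selected.

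Extending the scored lesions to all those seen on either scan would make this more informative. It is optional, because it may need lesion matching and an extra scoring step after the separate reads.

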#### 5.1.3 First PET/CT acquisition

Sixty minutes after FDG tracer injection, a standard clinical whole-body PET/CT scan is performed on the conventional or digital PET/CT scanner. (As mentioned in the study design, the PET scan order is randomized per week). For the first scan, the acquisition times are 1 and 2 minutes per bed position for patients with body weight up to 80 kilogram and from 81 kilogram respectively. To cover the whole-body region, on average 11 bed positions are required. This results in total PET

acquisition times of approximately 11 and 22 minutes for patients with body weight  $\leq 80$  kg and  $> 80$  kg respectively. Furthermore, attenuation CT acquisition takes around 5 minutes in all patients. Moreover, for many patients an additional diagnostic contrast-enhanced CT scan is acquired on the clinical PET/CT system with a total procedure time of approximately 15 minutes.

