#### **5.1.4 Second PET/CT acquisition (study procedure)**

Consecutively after the first PET/CT scan, an additional PET/CT scan is acquired on the second PET/CT system. To minimize the decrease in FDG present in the human body when performing the second PET/CT scan, the time between first and second PET/CT scan should be kept as short as possible. However, the amount of FDG present in the human body during the second PET/CT scan will be less as compared to the first PET/CT scan. Therefore, the acquisition time for second PET/CT scanning will equal to first PET/CT scan, plus a compensation for the radioactive decay. Due to differences in PET acquisition times and the acquisition of a diagnostic CT scan, there will be differences in delay time between patients. In general, patients can be divided in four groups for expected delay:

1. Patient bodyweight  $\leq 80$  kg and no diagnostic ceCT: delay  $\approx 21$  minutes
2. Patient bodyweight  $> 80$  kg and no diagnostic ceCT: delay  $\approx 32$  minutes
3. Patient bodyweight  $\leq 80$  kg and a diagnostic ceCT: delay  $\approx 36$  minutes
4. Patient bodyweight  $> 80$  kg and a diagnostic ceCT: delay  $\approx 47$  minutes

FDG has a half-life of 110 minutes. Using the formula for radioactive decay  $N(t) = N(0) \cdot 0.5^{T/T_{0.5}}$ , the percentage of FDG after the delay can be calculated. The correction factor is determined by calculating the inverse of the percentage of FDG, present after the delay. Based on this correction factor, the total acquisition time for the second PET/CT system can be calculated. Table 2 provides an indication of the scan times required for digital PET/CT scanning. As can be seen in this table, patients' bodyweight ( $\leq 80$  kg or  $> 80$  kg) is the main predicting factor whether the acquisition time on second PET takes approximately 20 minutes or approximately 35 minutes. Based on this estimation, we expect that the additional time for patients participating in this study will typically be 25 minutes but will not take more than 40 minutes.

**Table 2: Indications of total scan time on second PET/CT system, based on expected delays in four groups of patients.** The total scan time on second PET/CT includes the time for PET acquisition (with 11 bed positions (bp)) and attenuation CT acquisition.

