Patient group	Delay in minutes (≈)	Amount of FDG after delay (%)	Correction factor	Second PET, scan time per bp (s)	Second PET/CT scan time (min)
1	21	88%	1.14	60*1.14 = 68	18
2	32	82%	1.22	120*1.22 = 147	32
3	36	80%	1.25	60*1.25 = 75	19
4	47	74%	1.34	120*1.34 = 161	35

To provide an optimal comparison between conventional and digital PET/CT, we will use a patient-specific protocol for the second PET scan, based on the exact delay for each patient. This delay will be determined once the patient arrives in the room for the second PET/CT scan and will be used to set the final PET scan time per bed position for the second PET scan, for each patient separately.

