### **Normal tissue appearance**

When looking at the normal tissue appearance, we will perform a population-based comparison of average values in normal tissue uptake between conventional and digital PET/CT. Differences will be assessed using the Wilcoxon signed-rank test. It is expected that patient delay may influence normal tissue FDG-uptake. Therefore, we will study the presence of correlations between the amount of time-delay and differences in normal tissue uptake between conventional- and digital scans.

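### Scan order is counterbalanced by week but left out of every digital-versus-conventional test, which can cost power and, if a tumour group is unevenly split, adds bias

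*Combined protocol and SAP*

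**What the plan says.** **Design.** Section 3 says "The scan order will be randomized per week" and lists conventional first in week 1, then "Week 2: first scan on digital PET/CT, second scan on conventional PET/CT", and so on. As listed, this is alternation by calendar week. No balance of order is specified overall or within tumour type.

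**Timing.** The first scan starts "Sixty minutes after FDG tracer injection" (section 5.1.3). Section 5.1.4 and Table 2 (column "Delay in minutes") put the second scan about 21, 32, 36 or 47 minutes later, depending on body weight and whether a contrast-enhanced CT is made. The second acquisition is as long as the first "plus a compensation for the radioactive decay".

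**Analysis.** Section 7.1.1 says "For each patient separately, the diagnostic outcome for the conventional and digital PET/CT study will be compared", using sign, Wilcoxon signed-rank and McNemar tests. Section 7.1.2 (Lesion detectability) says "Differences between conventional and digital PET will be assessed using the Wilcoxon signed-rank test". No test in section 7 names scan order or period.

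**Delay.** Section 7.1.2 (Normal tissue appearance) says "It is expected that patient delay may influence normal tissue FDG-uptake" and plans to correlate the delay with the scanner difference. Section 5.2.4 is cautious about quantitative conclusions from the EANM reconstructions because of the delay, and section 5.3.2 describes those measurements as lesion-based.

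**The concern.** This is a two-period crossover analysed as a simple paired comparison. Longer bed times restore counts; they do not undo a change in tissue uptake between 60 minutes and about 81 to 107 minutes after injection. In the digital-minus-conventional difference, such a drift enters with a plus sign for patients scanned second on digital and a minus sign for those scanned first on digital.

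The weekly reversal protects the mean difference, but only as far as the two orders are equally filled in the group being tested. It does not protect the variance, because the pooled test treats the drift as random scatter. An analysis that uses order recovers that precision and removes the dependence on balance. What is at stake is mainly the quantitative lesion and normal-tissue comparisons, and to a lesser degree the primary staging comparisons in groups of 90, 90 and 45.

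**Working it through.** **1. The plan's own figures.** The FDG fraction left is 0.5^(delay/110), and the correction factor is its inverse.

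| Delay (min) | FDG left | Factor |
|---|---|---|
| 21 | 87.6% | 1.14 |
| 32 | 81.7% | 1.22 |
| 36 | 79.7% | 1.25 |
| 47 | 74.4% | 1.34 |

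These match Table 2, so the compensation is for physical decay alone.

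**2. Model.** For one patient, y = δ + d·s + e, where y is the digital-minus-conventional log difference, δ the scanner effect, d the drift between first and second scan, and s = +1 if digital is second, −1 if first. With q the share scanned second on digital:
- bias of the pooled mean = d(2q − 1)
- pooled SD = √(SD² + 4q(1 − q)d²)

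**3. Assumed inputs.** The documents give neither drift nor SD. Assumed: SD 0.15 on the log scale; d = 0.05 to 0.20; one value per patient; n = 81 (90 × 0.9, from the plan's allowance of 10% negative scans).

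**4. Even split.** Bias = d(2 × 0.5 − 1) = 0. The pooled SD rises from 0.15 to √(0.0225 + 0.01) = 0.18 at d = 0.10 and to √(0.0225 + 0.04) = 0.25 at d = 0.20. With an order term the standard error stays at 0.15/√81 = 0.0167, so a 5% effect gives z = 3.0 and power Φ(3.0 − 1.96) ≈ 85%. By simulation, for a 5% effect:

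| d | Pooled Wilcoxon | With order term |
|---|---|---|
| 0.05 | 79% | about 85% |
| 0.10 | 67% | about 85% |
| 0.15 | 46–48% | about 85% |
| 0.20 | 25–28% | about 85% |

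For a 10% effect, pooled power at n = 81 stays at about 99% or more. At n = 45, the size of the esophageal group, it is 97% at d = 0.10 and 75% at d = 0.20, against 99% with an order term.

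**5. Uneven split, identical scanners.** At 60:40 the bias is 0.2 × d, that is 0.01 to 0.04. The pooled Wilcoxon test rejects in about 7%, 14%, 21% and 23% at d = 0.05, 0.10, 0.15 and 0.20 (repeat runs differ by a point or two). With an order term it rejects in about 5%.

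**6. How often is a group split 60:40 or worse?** If each patient's order were an independent coin flip: 23% at n = 45, 7% at n = 81 to 90, and 34% for at least one of the three planned groups.

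**7. Primary sign test, identical scanners.** Exact rejection, with the later scan reading higher in 70–80% of discordant pairs:

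| Discordant patients | 50:50 | 60:40 | 65:35 |
|---|---|---|---|
| 20 to 40 | 1–3% | 3–5% | 5–12% |
| 80 | 1–2% | 6–9% | 13–26% |

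**8. The planned delay correlation.** With 225 patients, even orders, SD 0.15 and a real drift of 10% per 33 minutes, correlating the difference with unsigned delay gives about 0.00 on average, because the two orders cancel. Delay signed by order gives about 0.58.

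**The case against.** The weekly reversal is itself the control for order, and at balance it works: the mean difference is unbiased and the pooled test is conservative. That stands. A reader might infer that pooling biases the scanner comparison outright, or that drift swamps it. The documents support neither. Bias needs an uneven split, and swamping needs a drift that is large relative to the scanner effect, whereas no drift or SD is given.

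Nor do the documents show that an uneven split is likely. With weekly alternation and Poisson arrivals over an assumed 39 weeks, a 60:40 or worse split occurs in about 8% of runs at n = 81, 25% at n = 45 and 0.4% at n = 225. Averaged over the splits that arise, the pooled Wilcoxon error is about 4–6% at n = 81, close to nominal. Under assumed overdispersed weekly accrual it is 6–11%. The 7–23% therefore describes a trial that turns out 60:40; it is not the expected error rate.

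A reader might also infer that the primary sign tests are unsafe. That takes something like 80 discordant patients, nearly all of the 81 with malignancy, or a split beyond 60:40. The plan names an expected delay effect only for normal-tissue uptake, although its caution about the EANM measurements extends to lesion-based values.

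Two limits on the illustration also stand. It uses one value per patient, whereas the lesion analysis compares all lesions seen on both scans, so the figures do not describe that test exactly. It also generates one constant drift per order, while delay varies from 21 to 47 minutes, so an order indicator removes only the average drift.

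Finally, the plan is not silent on delay. But the normal-tissue correlation uses unsigned delay, the EANM remark is a caveat without an analysis, and the randomised reading order in section 5.2.2 deals with reader learning, not scan order.

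**Conclusion.** The point holds in a limited form. The plan reverses scan order and then does not use it, although it expects delay to affect uptake. With balanced orders the cost is precision: negligible if drift is small or the scanner effect is about 10% in a group of 81, substantial if the effect is nearer 5% and drift reaches 0.15 to 0.20. With an uneven tumour group there is also a bias of (2q − 1) × drift, which the plan neither prevents nor reports. For the primary sign tests the effect on false positives is small at plausible discordance.

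All of these sizes depend on an SD, drift and scanner effect that the documents do not supply; they show a range, not a finding about this trial. The change is worth making because it protects against both consequences at almost no cost.

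**What to change.** In sections 7.1.1 and 7.1.2, estimate the scanner effect with scan order as a term or stratum:
- **Quantitative measures:** regress the paired difference on order coded ±1, or on delay signed by order, and read the scanner effect from the intercept. Treat lesions as clustered within patient.
- **Ordinal and directional outcomes** (lesion counts, N, M and TNM status, reader scores) and paired accuracy: use an order-stratified rank or sign test of the Mainland-Gart type.
- **Normal-tissue correlation:** sign the delay by scan order.
- **Reporting:** give the order split and the order-specific results by tumour type, next to the pooled result. Describe the allocation as weekly alternation if that is what is done.

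The cost is SAP wording and one degree of freedom. The scanner, FDG administration time and scan start time are already on the data form (Figure 5, section 5.2.1), so order and delay can be derived. No scan, procedure or patient is added.
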